1.3 STUDY RATIONALE AND BENEFIT-RISK ASSESSMENT

The rationale for conducting this Phase IIa proof-of-activity study of MTPS9579A in patients with asthma requiring ICS and a second controller is to evaluate efficacy, safety, pharmacokinetics, and pharmacodynamics in a relevant patient population. Inhibiting tryptase with MTPS9579A is anticipated to block airway inflammation downstream of mast cell activation across all asthma types. The goals of this study are to determine the impact of monthly treatment with MTPS9579A on patients' signs and symptoms of asthma using a combination of patient-reported measures and functional measures of exacerbation and to continue to understand safety and the PK/PD relationships of MTPS9579A and tryptase.

The safety profile of MTPS9579A in healthy volunteers from the Phase Ia/b study (GA40396) is described in Section 1.2 and in the MTPS9579A Investigator's Brochure. Risks in patients with asthma are unknown, but the favorable safety profile in healthy volunteers supports further development in patients with asthma. The safety plan for patients in this study is described in Section 5.1.

2. OBJECTIVES AND ENDPOINTS

This study will evaluate the efficacy, safety, and pharmacokinetics of MTPS9579A compared with placebo in patients with uncontrolled asthma despite the use of ICS and

a second controller. Specific objectives and corresponding endpoints for the study are outlined below.

2.1 EFFICACY OBJECTIVES

2.1.1 Primary Efficacy Objective

The primary efficacy objective for this study is to evaluate the efficacy of MTPS9579A compared with placebo on the basis of the following endpoint:

- Time to first CompEx event (Fuhlbrigge et al. 2017), a composite endpoint defined as time from randomization to first asthma exacerbation or diary worsening during the 48-week double-blind treatment period (from the randomization visit [Week 2] to end of treatment [Week 50]). Asthma exacerbations and diary worsening are defined as follows:

Asthma exacerbations are assessed by the investigator and defined as new or increased asthma symptoms (wheezing, coughing, dyspnea, chest tightness, and/or nighttime awakenings due to these symptoms) that result in one or both of the following:

- Hospitalization or an emergency department or urgent care visit requiring administration of systemic corticosteroid treatment
- Treatment with systemic (IV, intramuscular [IM], or oral) corticosteroids for ≥ 3 days or a long-acting depot corticosteroid preparation with a therapeutic effectiveness of ≥ 3 days
- Diary worsening is based on the occurrence of prespecified changes (deteriorations) in a subset of the following six parameters: morning peak expiratory flow rate (PEFR), evening PEFR, morning symptom score, evening symptom score, morning short-acting rescue therapy use, and evening short-acting rescue therapy use. A detailed definition of diary worsening is provided in Section 6.4.1.

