2.1.2 Secondary Efficacy Objective

The secondary efficacy objective for this study is to evaluate the efficacy of MTPS9579A compared with placebo on the basis of the following endpoints:

- Rate of asthma exacerbations (as defined in primary efficacy objective and assessed by the investigator) during the 48-week double-blind treatment period
- Time to first asthma exacerbation during the 48-week double-blind treatment period
- Absolute and relative change from randomization in pre-bronchodilator forced expiratory volume in 1 second (FEV₁; liters) at Week 50
- Absolute and relative change from randomization in fractional exhaled nitric oxide (FeNO) at Week 50

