2.1.3 Exploratory Efficacy Objective

The exploratory efficacy objective for this study is to evaluate the efficacy of MTPS9579A compared with placebo on the basis of the following endpoints:

- Rate of severe asthma exacerbations during the 48-week double-blind treatment period, defined as asthma symptoms requiring hospitalization or resulting in death attributed to asthma
- Absolute change from randomization in pre-bronchodilator FEV₁ (percentage predicted) at Week 50
- Absolute change from randomization in patient-reported daytime asthma symptom severity, as measured by a daily symptom diary (as defined in primary efficacy objective), at Week 50
- Absolute change from randomization in patient-reported nighttime asthma symptom severity, as measured by a daily symptom diary (as defined in primary efficacy objective), at Week 50
- Absolute change from randomization in patient-reported number of puffs of short-acting rescue inhaler or number of times nebulizer was used at Week 50
- Absolute and relative change from randomization visit in provocative dose of methacholine causing a 20% drop in FEV₁ (PD₂₀) as a measure of airway hyper-responsiveness at Week 30, in patients who consent to this optional assessment at select sites

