5.3.5.8 Deaths

All deaths that occur during the protocol-specified adverse event reporting period (see Section [5.3.1](#)), regardless of relationship to study drug, must be recorded on the Adverse Event eCRF and immediately reported to the Sponsor (see Section [5.4.2](#)). This includes death attributed solely to exacerbation of asthma.

Death should be considered an outcome and not a distinct event. The event or condition that caused or contributed to the fatal outcome should be recorded as the single medical concept on the Adverse Event eCRF. Generally, only one such event should be reported. If the cause of death is unknown and cannot be ascertained at the time of reporting, "**unexplained death**" should be recorded on the Adverse Event eCRF. If the cause of death later becomes available (e.g., after autopsy), "unexplained death" should be replaced by the established cause of death. The term "**sudden death**" should not be used unless combined with the presumed cause of death (e.g., "sudden cardiac death").

If the death is attributed solely to asthma exacerbation, "asthma exacerbation" should be recorded on the Adverse Event eCRF.

Deaths that occur after the adverse event reporting period should be reported as described in Section [5.6](#).

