6.4.1 Primary Efficacy Endpoint

The primary efficacy endpoint is time to first CompEx event, defined as time from randomization to first asthma exacerbation or diary worsening during the 48-week double-blind treatment period. Asthma exacerbations and diary worsening are defined as follows:

- Asthma exacerbations are assessed by the investigator and defined as new or increased asthma symptoms (wheezing, coughing, dyspnea, chest tightness, and/or nighttime awakenings due to these symptoms) that result in one or both of the following:
 - Hospitalization or an emergency department or urgent care visit requiring administration of systemic corticosteroid treatment
 - Treatment with systemic (IV, IM, or oral) corticosteroids for \geq 3 days or a long-acting depot corticosteroid preparation with a therapeutic effectiveness of \geq 3 days
- Diary worsening is based on the occurrence of prespecified changes (deteriorations) in the following six parameters: morning PEFR, evening PEFR, morning symptom score, evening symptom score, morning short-acting rescue therapy use, and evening short-acting rescue therapy use. Deterioration criteria, defined as either a change from baseline (threshold) or worsening of a certain magnitude (slope) over 5 consecutive days, are presented for each parameter in [Appendix 8](#). Diary worsening is defined as occurrence of one or both of the following scenarios:

- Patient meets threshold deterioration criterion (i.e., prespecified change from baseline) for PEFR (morning and/or evening) and at least one other parameter (i.e., morning symptom score, evening symptom score, morning rescue therapy use, and/or evening rescue therapy use) on 2 consecutive days.
- Patient meets threshold deterioration criterion (i.e., prespecified change from baseline) for one parameter on 2 consecutive days and slope deterioration criterion (i.e., prespecified change over 5 consecutive days calculated via univariate linear regression) for all six parameters.

For the purposes of determining whether the threshold deterioration criteria are met, baseline levels are calculated for each individual as the mean over the 10 planned sessions conducted prior to time of randomization for each of the diary variables.

In the event that the first diary worsening scenario is met (i.e., threshold met in two parameters), the diary worsening event will start on the first of the 2 consecutive days (defined as Event Days 0 and 1).

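### Asthma death counts as a severe exacerbation but not as an asthma exacerbation, so a sudden asthma death may add no event to CompEx or to either secondary exacerbation endpoint

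*Protocol*

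**What the plan says.** - **Exacerbation definition** (Protocol 2.1.1, repeated in 6.4.1 and the synopsis). Symptoms must lead to one or both of two outcomes. The first is "Hospitalization or an emergency department or urgent care visit requiring administration of systemic corticosteroid treatment". The second is systemic corticosteroids for at least 3 days "or a long-acting depot corticosteroid preparation with a therapeutic effectiveness of" at least 3 days. The list is closed and death is not on it. Section 5.3.5.10 also describes an exacerbation in terms of corticosteroids and refers back to 2.1.1.
- **Endpoints that use it.** CompEx is "a composite endpoint defined as time from randomization to first asthma exacerbation or diary worsening during the 48-week double-blind treatment period". The secondary endpoints in 2.1.2 are "Rate of asthma exacerbations (as defined in primary efficacy objective and assessed by the investigator) during the 48-week double-blind treatment period" and "Time to first asthma exacerbation during the 48-week double-blind treatment period". SAP Outputs 3.1 to 3.3 add no death component, and Outputs 3.2 and 3.3 describe the event as protocol-defined.
- **Severe exacerbation** (Protocol 2.1.3, 6.4.3; exploratory): "defined as asthma symptoms requiring hospitalization or resulting in death attributed to asthma".
- **Incomplete follow-up.** Section 6.4.1 uses observed events without imputation. Section 6.4.2 ends time at risk at treatment completion or discontinuation. Neither mentions death, and the SAP gives no rule for it.
- **Recording.** Section 5.3.5.8 says "If the death is attributed solely to asthma exacerbation", that term goes on the Adverse Event eCRF. Section 4.5.12 sends efficacy exacerbations to a separate dedicated eCRF.

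**The concern.** A severe form of an event should be contained in the event. Here it is not: an asthma death can be a severe exacerbation, and be coded as an asthma exacerbation in the safety data, without being an exacerbation for efficacy.

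The case that falls through is an abrupt asthma death before any hospital attendance or corticosteroid course. If it is left out, the patient drops from the risk set without an event, as though follow-up had ended for a reason unrelated to asthma. That favours the arm in which the death occurs. The two secondary exacerbation endpoints are more exposed than CompEx because they have no diary route.

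The protocol itself foresees asthma death (2.1.3, 5.3.5.8). It enrols patients with at least two exacerbations in the previous year (4.1.1.1), so the case is not purely theoretical.

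**Working it through.** **Step 1. Follow an asthma death through each definition.**

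| Course before death | Severe exacerbation | Exacerbation rate, time to first exacerbation | CompEx |
|---|---|---|---|
| Hospital, ED or urgent-care visit with systemic corticosteroids, or a qualifying corticosteroid course | Counts | Counts | Counts |
| No hospital care or corticosteroids, but diary worsening recorded | Counts | Fatal episode adds nothing | Counts through the diary |
| Earlier exacerbation during treatment, then sudden death | Counts | Earlier event counts; fatal episode adds nothing | Already has an event |
| Sudden death, no earlier exacerbation or diary worsening | Counts | No event | No event |

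The second row follows from the first diary scenario in 6.4.1: "Patient meets threshold deterioration criterion (i.e., prespecified change from baseline) for PEFR (morning and/or evening) and at least one other parameter", on 2 consecutive days. The other scenario needs one threshold met on 2 consecutive days plus a slope criterion in all six parameters. Neither needs hospital care or corticosteroids. Both need at least 2 days of recorded deterioration, so an abrupt death is not caught.

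**Step 2. Precision at the planned interim.** No figure in the plan rests on this definition, so there is nothing to reproduce. Section 6.1 gives only the 51 events, and the remainder is redacted. With 51 events (6.9.1) and roughly equal arms:

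- SE(log HR) = 2/√51 = 0.280
- 95% CI factors = exp(±1.96 × 0.280) = 0.58 to 1.73
- With 52 events: SE = 2/√52 = 0.277, factors 0.58 to 1.72

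**Step 3. Effect of one or two uncounted deaths.** A rough figure is one event out of 51/2 = 25.5 per arm, or 1/25.5 = 3.9%. A Cox simulation checks this. Its inputs are 65 placebo and 69 active patients (SAP Output 1.1), 48 weeks, and exponential times with hazards set to give about 51 events. Each case has 400 runs. One or two otherwise event-free patients in one arm die at a random time, and the deaths are scored first as censored and then as events. The numbers of deaths and the true hazard ratios are assumptions.

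| True HR | Deaths (arm) | HR, deaths censored | HR, deaths counted | Ratio |
|---|---|---|---|---|
| 1.0 | 1 (active) | 1.018 | 1.057 | 1.039 |
| 1.0 | 1 (placebo) | 0.962 | 0.925 | 0.961 |
| 1.0 | 2 (active) | 1.027 | 1.106 | 1.077 |
| 1.0 | 2 (placebo) | 0.979 | 0.904 | 0.924 |
| 0.65 | 1 (active) | 0.652 | 0.682 | 1.047 |
| 0.65 | 1 (placebo) | 0.651 | 0.629 | 0.966 |
| 0.65 | 2 (active) | 0.674 | 0.736 | 1.092 |
| 0.65 | 2 (placebo) | 0.628 | 0.587 | 0.934 |

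The paired ratio is the result to read; the levels vary with the random draws. One death moves the hazard ratio by about 3-5%. On the log scale the largest single-death shift is ln(1.047) = 0.046. The half-width of the interval is 1.96 × 0.280 = 0.549, so the shift is 0.046/0.549 = 8% of it.

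**The case against.** **A reader might infer that every patient who dies of asthma before hospital or corticosteroids is event-free on the primary endpoint.** The documents do not support that. CompEx takes the first exacerbation or diary worsening, so an earlier event of either kind, or a final decline recorded over 2 days, already counts. Only a sudden death with no earlier event is missed.

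**Nor do the documents say that the death is scored as the best outcome.** Censoring at death is inferred from the use of observed events without imputation. It is not written. A patient censored at death also leaves the risk set and is not credited with 48 event-free weeks.

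**The recording rules leave some room.** Exacerbations are investigator-assessed, and an asthma death is coded as one on the Adverse Event eCRF. The documents do not say whether it is also entered on the dedicated form. This makes practice uncertain, but the definition that the efficacy outputs use still has no route for death.

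**An asthma admission managed without corticosteroids is a weaker case.** It is excluded only if the corticosteroid condition in the first route attaches to hospitalization as well as to ED and urgent-care visits. On the other reading it qualifies. It should be clarified, not counted as an established gap.

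**Composition and timing.** CompEx comes from a cited source that cannot be checked here, and adding death could depart from it. The change would also be late: enrollment has ended, arm sizes appear in SAP Output 1.1, and the SAP describes its outputs as unblinded. The timing objection stands as a reason for transparency. It does not justify leaving the definitions inconsistent.

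**Size.** The trial's stated goal is estimation, and the effect is small. In the SAP text available, Section 3 also has no severe-exacerbation output, so the mismatch would not show between two efficacy tables. Equally, the one endpoint that counts asthma death has no output there.

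**Conclusion.** The definitions do not nest, and this follows from the stated rule itself. Read literally, an asthma death before hospital care or systemic corticosteroids is not an event for the exacerbation rate or for time to first exacerbation. It is not one for CompEx either, although an earlier exacerbation or diary worsening already gives the patient a CompEx event. How the patient is then handled is unstated.

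The consequence is minor. It is nil if no such death occurs. Otherwise it is about 3-5% on the CompEx hazard ratio per death and 7-9% for two deaths in one arm, in favour of the arm with the deaths, under the assumptions above. The documents give no expected asthma death rate. The 51 events are the interim count, so the effect per death would be smaller if the final analysis has more events. This is a worthwhile tidy-up and does not threaten the trial's conclusions.

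**What to change.** 1. In Protocol 2.1.1, 6.4.1 and the synopsis, add death attributed to asthma as a qualifying outcome of an asthma exacerbation. Date it at symptom onset if known, and otherwise at the date of death; the second part is needed for an unwitnessed death.
2. In the SAP, state that every event meeting the severe definition also counts as an exacerbation in Outputs 3.1 to 3.3, and that other deaths are censored at the date of death.
3. State whether the corticosteroid condition in the first route applies to hospitalization, so that the two definitions also agree on admissions.
4. Document whether any event affected by these changes is already known. If one is, report the results under both derivations.

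The cost is one clause in the definition and a few derivation lines. No new data are needed, because deaths and hospitalized adverse events are already recorded (5.3.5.8, 5.3.5.11). The downside is a late change to the primary event definition, which step 4 makes visible.

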2.1.2 Secondary Efficacy Objective

The secondary efficacy objective for this study is to evaluate the efficacy of MTPS9579A compared with placebo on the basis of the following endpoints:

- Rate of asthma exacerbations (as defined in primary efficacy objective and assessed by the investigator) during the 48-week double-blind treatment period
- Time to first asthma exacerbation during the 48-week double-blind treatment period
- Absolute and relative change from randomization in pre-bronchodilator forced expiratory volume in 1 second (FEV₁; liters) at Week 50
- Absolute and relative change from randomization in fractional exhaled nitric oxide (FeNO) at Week 50

2.1.3 Exploratory Efficacy Objective

The exploratory efficacy objective for this study is to evaluate the efficacy of MTPS9579A compared with placebo on the basis of the following endpoints:

- Rate of severe asthma exacerbations during the 48-week double-blind treatment period, defined as asthma symptoms requiring hospitalization or resulting in death attributed to asthma
- Absolute change from randomization in pre-bronchodilator FEV₁ (percentage predicted) at Week 50
- Absolute change from randomization in patient-reported daytime asthma symptom severity, as measured by a daily symptom diary (as defined in primary efficacy objective), at Week 50
- Absolute change from randomization in patient-reported nighttime asthma symptom severity, as measured by a daily symptom diary (as defined in primary efficacy objective), at Week 50
- Absolute change from randomization in patient-reported number of puffs of short-acting rescue inhaler or number of times nebulizer was used at Week 50
- Absolute and relative change from randomization visit in provocative dose of methacholine causing a 20% drop in FEV₁ (PD₂₀) as a measure of airway hyper-responsiveness at Week 30, in patients who consent to this optional assessment at select sites

2.2 SAFETY OBJECTIVE

The safety objective for this study is to evaluate the safety of MTPS9579A compared with placebo on the basis of the following endpoints:

- Incidence and severity of adverse events, with severity determined according to the WHO Toxicity Grading Scale
- Change from randomization visit in physical examination findings
- Change from randomization visit in vital signs
- Change from randomization visit in ECG parameters
- Change from randomization visit in clinical laboratory results

2.3 PHARMACOKINETIC OBJECTIVES

The PK objective for this study is to characterize the MTPS9579A PK profile on the basis of the following endpoint:

- Serum concentration of MTPS9579A at specified timepoints

The exploratory PK objective for this study is to characterize concentrations of MTPS9579A in nasal mucosal lining fluid and to evaluate potential relationships between

drug exposure and the efficacy and safety of MTPS9579A on the basis of the following endpoints:

- Relationship between serum concentration, nasal mucosal lining fluid concentration, or PK parameters for MTPS9579A and efficacy or PD endpoints
- Relationship between serum concentration, nasal mucosal lining fluid concentration, or PK parameters for MTPS9579A and safety endpoints

2.4 IMMUNOGENICITY OBJECTIVES

The immunogenicity objective for this study is to evaluate the immune response to MTPS9579A on the basis of the following endpoint:

- Prevalence of anti-drug antibodies (ADAs) during the study relative to the prevalence of ADAs at the randomization visit

The exploratory immunogenicity objective for this study is to evaluate potential effects of ADAs on the basis of the following endpoint:

- Relationship between ADA status and efficacy, safety, or PK/PD endpoints

2.5 BIOMARKER OBJECTIVE

The exploratory biomarker objective for this study is to identify and/or evaluate biomarkers that are predictive of response to MTPS9579A (i.e., predictive biomarkers), can provide evidence of MTPS9579A activity (i.e., PD biomarkers), or can increase the knowledge and understanding of disease biology and drug safety, on the basis of the following endpoints:

- Change from the randomization visit in biomarker levels in nasal mucosal lining fluid, urine, and serum samples
- Relationship among biomarker levels in nasal mucosal lining fluid, urine, and serum samples
- Relationship between biomarkers in nasal mucosal lining fluid, urine, and serum (listed in Section 4.5.9) and efficacy, safety, PK, and immunogenicity endpoints
- Rate of asthma exacerbations within subgroups defined by blood eosinophils during the 48-week double-blind treatment period
- Time to first CompEx event (as defined in primary efficacy objective) within subgroups defined by blood eosinophils during the 48-week double-blind treatment period
- Rate of asthma exacerbations in subgroups defined by mutations in the genes encoding tryptase (*TPSAB1* and *TPSB2*) during the 48-week double-blind treatment period
- Time to first CompEx event (as defined in primary efficacy objective) in subgroups defined by mutations in the genes encoding tryptase (*TPSAB1* and *TPSB2*) during the 48-week double-blind treatment period

3. STUDY DESIGN

3.1 OVERVIEW OF THE STUDY DESIGN

This is a Phase IIa, randomized, placebo-controlled, double-blind, multicenter, two-arm study of MTPS9579A compared with placebo as an add-on therapy in patients with uncontrolled moderate to severe asthma who are receiving daily ICS therapy and at least one of the following additional controller medications: LABA, leukotriene modulator (leukotriene modifier [LTM] or leukotriene receptor antagonist [LTRA]), long-acting muscarinic antagonist (LAMA), or long-acting theophylline preparation. The study *initially was to* randomize approximately 160 patients at approximately 55 sites globally. *However, as of March 2021, study enrollment was halted with 134 patients enrolled, and in August 2021, a decision was made to permanently halt further enrollment.*

This study will consist of a 12–28 day screening period, a 2-week single-blind placebo run-in period, a 48-week double-blind treatment period, a safety follow-up visit at Week 54, and a safety follow-up phone call at Week 58. During the screening period, patients must demonstrate acceptable inhaler, peak flow meter, and spirometry techniques, in addition to compliance with required, twice-daily use of an electronic diary (eDiary) for answering questions related to asthma symptoms, PEFR, and short-acting rescue therapy use (see Section 4.5.8). Patients who fail to meet eligibility criteria during the screening period will be permitted to re-screen once as described in Section 3.1.1.

Patients who meet enrollment criteria for the run-in period will receive one single-blind dose of placebo (Week 0) to allow for the evaluation of variability in asthma control. At the randomization visit (Week 2), patients must meet additional eligibility criteria for the double-blind treatment period that includes continued compliance with required, twice-daily use of the eDiary (see Section 4.1.1.2).

[figure not shown]
Patients will be randomized in a 1:1 ratio to receive MTPS9579A (1800 mg IV Q4W) or placebo as described in Section 4.2. Study drug will be administered by IV infusion at the randomization visit (Week 2), Week 6, and every 4 weeks thereafter through Week 46.

During the treatment period, twice-daily assessment of asthma-related symptoms, PEFR, and use of short-acting rescue therapy (see Section 4.5.8) will continue to be performed at home and recorded in the eDiary. More detailed assessments, including spirometry and FeNO measurements, will be performed during scheduled site visits. All patients will undergo PK, biomarker, and ADA sampling. An additional exploratory efficacy assessment, the methacholine challenge test to assess airway reactivity, will be conducted at select sites in a subset of patients (approximately 20 patients/study arm) who consent to this option and meet additional eligibility criteria (see Sections 4.1.1.3 and 4.5.14).

A planned interim analysis will take place once approximately 51 patients have experienced a CompEx event in the 48-week, double-blind treatment period. The expected timing of this planned interim analysis is approximately 60 weeks after the first patient is randomized. *An optional interim analysis may also be conducted. These interim analyses will be conducted for potential enrollment decisions (e.g., temporary or permanent enrollment halt, change to number of total randomized patients), for early study termination, or for administrative purposes (e.g., planning of future studies) (see Section 6.9).*

[Figure 1](#) presents an overview of the study design. A schedule of activities is provided in [Appendix 1](#).

Figure 1 Study Schema

EOS=end of study; EOT=end of treatment; F/U=safety follow-up; ICS=inhaled corticosteroids; T/C=telephone call; Q4W=every 4 weeks.

^a Screening period is 12–28 days.

